### Definition of Overall Response Using irRC

Overall response using irRC will be based on these criteria:

**Immune-Related Complete Response (irCR):** Complete disappearance of all tumor lesions (index and non-index together with no new measurable/unmeasurable lesions) for at least 4 weeks from the date of documentation of complete response.

**Immune-Related Partial Response (irPR):** The sum of the products of the two largest perpendicular diameters of all index lesions is measured and captured as the SPD baseline. At each subsequent tumor assessment, the sum of the products of the two largest perpendicular diameters of all index lesions and of new measurable lesions are added together to provide the Immune Response Sum of Product Diameters (irSPD). A decrease, relative to baseline of 50% or greater is considered an immune Partial Response (irPR).

The decrease must be confirmed 4 weeks later.

**Immune-Related Stable Disease (irSD):** irSD is defined as the failure to meet criteria for immune complete response or immune partial response, in the absence of progressive disease.

**Immune-Related Progressive Disease (irPD):** It is recommended in difficult cases to confirm PD by serial imaging. Any of the following will constitute progressive disease:

- At least a 25% increase in the sum of the products of all index lesions and new measurable lesions (irSPD) over the nadir SPD calculated for the index lesions. PD must be confirmed 4 weeks later.

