1.4.2 EXPLORATORY EFFICACY ENDPOINTS

Per protocol, all efficacy analyses are exploratory. The main efficacy endpoint is the ORR, defined as the proportion of subjects in the analysis population who have complete response (CR) or partial response (PR) at any time during the study using irRC ([Wolchok et al, 2009](#)).

Additional efficacy endpoints include:

- Duration of response (DOR), defined as the time from first response to disease progression in subjects who achieve a PR or better, based on assessment by irRC.
- Overall response rate and DOR based on response evaluation criteria in solid tumors version 1.1 (RECIST 1.1) ([Eisenhauer et al, 2009](#)).

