1.6.2 STATISTICAL METHODS FOR EXPLORATORY EFFICACY ANALYSES

Efficacy will be evaluated in the FAS population. For the key efficacy endpoint of ORR based on irRC, the point estimate, and 95% CI (as determined by the upper and lower 97.5% one-sided

confidence bounds) will be provided using an exact binomial distribution. Subjects without response data will be counted as non-responders.

DOT will be summarized using Kaplan-Meier (KM) method in all responders.

An outline of the key efficacy analysis strategy is presented in Table 1.

Table 1 Primary Analysis Strategy for Efficacy Endpoints

Endpoint/Variable (Description, Time Point)	Statistical Method	Analysis Population	Missing Data Approach
Primary:			
Overall irRC response rate based on investigator assessment	Exact test of binomial parameter	FAS	Subjects with missing data are considered non-responders
Secondary:			
Overall RECIST 1.1 response rate based on investigator assessment	Exact methods for binomial parameter	FAS	Subjects with missing data are considered non-responders
Response duration (RECIST 1.1)	Summary statistics using Kaplan-Meier method	All responders	Non-responders are excluded in analysis
Response duration (irRC)	Summary statistics using Kaplan-Meier method	All responders	Non-responders are excluded in analysis
Exploratory:			
Overall irRC response rate and RECIST 1.1 response rate based on investigator assessment without requiring confirmatory scans for (ir)CR/PR responses	Exact methods for binomial parameter	FAS	Subjects with missing data are considered non-responders

CR = complete response; FAS = full analysis set; ir = immune related; irRC = immune-related response criteria; PR = partial response; RECIST = response evaluation criteria in solid tumors

Details of the exploratory biomarker analysis strategy will be documented in the sSAP.

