1.9 RESPONSE CRITERIA

1.9.1 IMMUNE RELATED RESPONSE CRITERIA

For all patients who experience disease progression on study, the date noted for disease progression is the time of the scan where it is originally detected, and not the following date of the confirmatory scan. If a scan was not available, the date of disease progression was identified by the Investigator.

Definitions of measurable and non-measurable disease

Measurable disease: Neoplastic masses that can be precisely measured in 2 in-plane perpendicular diameters. Both the longest diameter and the longest perpendicular must be greater than or equal to 10 mm or 2 times the axial slice thickness, whichever is greater. Lymph nodes must have a short-axis line-length of ≥ 15 mm. Malignant lymph nodes must be measurable in 2 perpendicular diameters. Both the longest diameter and the longest perpendicular must be greater than or equal to 15 mm or 2 times the axial slice thickness. The quantitative endpoint will be defined as the product of the longest diameter with its longest perpendicular.

Non-measurable disease: Non-measurable lesions are those that are not suitable for quantitative assessment over time. These include:

1. Neoplastic masses that are too small to measure, because their longest uninterrupted diameter or longest perpendicular are less than 10 mm or two (2) times the axial slice thickness.
2. Neoplastic masses whose boundaries cannot be distinguished. This includes masses that cannot be demarcated from surrounding tissue because of inadequate contrast, masses with overly complex morphology, or those with highly heterogeneous tissue composition.
3. Other types of lesions that are confidently felt to represent neoplastic tissue but difficult to quantify in a reproducible manner. These include bone metastases, leptomeningeal metastases, malignant ascites, pleural/pericardial effusions, inflammatory breast disease, lymphangitis cutis/pulmonis, cystic lesions, ill-defined abdominal masses, etc.

For irRC, only target lesions selected at baseline and measurable new lesions are taken into account.

At the baseline tumor assessment, the sum of the products of the two largest perpendicular diameters (SPD) of all **index lesions** (5 lesions per organ, up to 10 visceral lesions and 5

cutaneous index lesions) is calculated.

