At each subsequent tumor assessment, the SPD of the index lesions and of new, measurable lesions ($\geq 5 \times 5$ mm; up to 5 new lesions per organ: 5 new cutaneous lesions and 10 visceral lesions) are added together to provide the total time-point **tumor burden**.

Overall response using irRC:

- Complete Response (irCR): Complete disappearance of all tumor lesions (whether measurable or not, and no new lesions). CR must be confirmed by repeated, consecutive assessments made no less than 4 weeks from the date first documented.
- Partial Response (irPR): $\geq 50\%$ decrease in tumor burden compared with baseline in two observations at least 4 weeks apart.
- Stable Disease (irSD): Failure to meet criteria for irCR or irPR, in absence of irPD.
- Progressive Disease (irPD): At least 25% increase in SPD relative to nadir (minimum recorded tumor burden) Confirmation by a repeat, consecutive assessment no less than 4 weeks from the data first documented.
- Non-index lesions contribute to defining irCR (complete disappearance required).

Immune-related response criteria for the current protocol was adopted from [Wolchok et al, 2009](#).

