1.9.3 ADDITIONAL EXPLORATORY RESPONSE EVALUATION CRITERIA

Because of the exploratory nature of the study, some subjects may not have had confirmatory scans prior to exposure to subsequent anti-cancer therapies. Therefore, both irRC and RECIST version 1.1 will be applied without the requirement for confirmatory scans for irCR/irPR and for CR/PR for irRC and RECIST version 1.1, respectively.

Summary statistics comparing the 2 methods of response criteria application (confirmed vs. unconfirmed response) may be calculated for qualitative comparisons.

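### Duration of response has progression as its only stated end, so deaths and, under irRC, unconfirmed progressions can go uncounted and DOR can be overstated

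*SAP*

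**What the plan says.** SAP 1.4.2 makes DOR an additional exploratory endpoint, "defined as the time from first response to disease progression in subjects who achieve a PR or better", and applies it under a second set of criteria as well: "Overall response rate and DOR based on response evaluation criteria in solid tumors version 1.1". SAP 1.6.2 gives the method: "DOT will be summarized using Kaplan-Meier (KM) method in all responders", where the abbreviation appears to be a slip for DOR. The only data-handling entry for DOR in SAP Table 1 is "Non-responders are excluded in analysis".

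For irRC progression (irPD), SAP 1.9.1 requires "Confirmation by a repeat, consecutive assessment no less than 4 weeks from the data first documented". Protocol 11.7.1 agrees: "PD must be confirmed 4 weeks later". On dating, SAP 1.9.1 says that "the date noted for disease progression is the time of the scan where it is originally detected", and that the investigator supplies the date when there was no scan. SAP 1.9.2 only cites RECIST 1.1 and adds no rule on confirming progression.

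SAP 1.9.3 recognises that some subjects may have moved to another anticancer therapy before a confirmatory scan. Its response is to apply both criteria "without the requirement for confirmatory scans for irCR/irPR and for CR/PR". Progression is not included in that waiver.

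**The concern.** Two kinds of terminal event can fall outside the definition.

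- **Death without documented progression.** It is not named as an event, so in a Kaplan-Meier analysis the patient leaves as a censored observation. That treats the patient as still at the same risk of losing response as those who remain, which is hard to defend for a death in unresectable, anti-PD-1-resistant melanoma.
- **irPD never re-assessed (irRC only).** Read literally, such a progression does not qualify. The protocol makes this situation plausible. Another treatment modality takes the patient off study (11.2), patients with progression are followed by chart review only (11.3), and later imaging is every 2 to 3 months at the investigator's discretion (11.6.3).

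If these patients are censored when they could have been counted, the DOR curve can only rise or stay where it is. With very few responders, one such patient can move the median, and the reported durability would then depend partly on an unstated convention.

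**Working it through.** **Nothing to reproduce.** The documents state no DOR figure, assumed median, event count, deaths among responders, unconfirmed irPDs or switches of therapy. All durations below are assumptions that show size only.

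**Inputs.** Treated patients: 3 × 4 cohorts = 12 (SAP 1.1). Responders: assumed four. Protocol 6.2.4 reports 4 of 12, but counts responses in injected lesions and does not call them overall irRC responders.

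**Formula.** S(t) is the product of (1 − d/n) over event times, with d events among n at risk. The median is the first time that S(t) is 0.50 or less.

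**Check 1: an early death.** Four responders: death at 3 months, progression at 6 and 9, ongoing at 12.

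- Death counted: S(3) = 1 − 1/4 = 0.75; S(6) = 0.75 × (1 − 1/3) = 0.50. Median 6 months.
- Death censored: three at risk at 6 months, S(6) = 1 − 1/3 = 0.667; S(9) = 0.667 × (1 − 1/2) = 0.333. Median 9 months.

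The ratio is 9/6 = 1.5. If the software takes the midpoint of the flat stretch when S is exactly 0.50, the first figure is (6 + 9)/2 = 7.5 and the contrast is 7.5 against 9: smaller, same direction. An unconfirmed irPD at 3 months, censored there, gives the same arithmetic.

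**Check 2: which event is lost matters.** Terminal events at 3, 6, 9 and 12 months. All counted: S(6) = 0.50, median 6.

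- First uncounted: S(6) = 0.667, S(9) = 0.333, median 9.
- Second uncounted: S(3) = 0.75, S(9) = 0.75 × (1 − 1/2) = 0.375, median 9.
- Third or fourth uncounted: S(6) is still 0.50, median 6.

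**Check 3: a general scale.** With exponential durations and a share s of terminal events censored, the counted hazard is (1 − s) times the true one, so the median is multiplied by 1/(1 − s): 1.11, 1.25, 1.43 and 2.00 for s = 10%, 20%, 30% and 50%. For s = 0 there is no change.

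**Check 4: later therapy or resection.** The SAP has no rule here, so the possible rules are compared. Four responders: progression at 4 months; resection at 3 followed by progression at 6; progression at 9; ongoing at 12.

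- Clock runs on: S(4) = 0.75, S(6) = 0.75 × (1 − 1/3) = 0.50. Median 6.
- Censored at resection: S(4) = 1 − 1/3 = 0.667, S(9) = 0.667 × (1 − 1/2) = 0.333. Median 9.
- Resection counted as the end: S(3) = 0.75, S(4) = 0.75 × (1 − 1/3) = 0.50. Median 4.

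The effect of this missing rule therefore has no fixed direction.

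**The case against.** Several points on the other side have weight.

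- **Consequence.** All efficacy is exploratory, there are no formal hypotheses (SAP 1.7), no inference is to be drawn (SAP 1.8), and the primary DLT endpoint is untouched. This stands and limits the weight of the point.
- **Censoring is inferred.** The SAP gives no DOR censoring rule. True, but a Kaplan-Meier summary with progression as the only event leaves censoring as the ordinary treatment of a death.
- **The irPD gap is softer than it looks.** The DOR definition speaks of disease progression rather than confirmed irPD. The investigator can supply a date when no scan exists. Protocol 11.7.1 recommends confirmation in difficult cases and also makes it mandatory, which sit badly together. These points narrow the gap but do not close it: the dating rule says when a progression is placed, not whether an unconfirmed one counts.
- **Scope.** The confirmation issue is confined to irRC, since the SAP sets no such requirement for RECIST 1.1. This stands.

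A reader might also infer that later therapy does not stop the DOR clock and that every gap pushes DOR upward. The documents do not support this. They are silent on later therapy and resection: Protocol 11.2 takes such patients off study, while 11.3 still follows them for progression. Check 4 shows that censoring at resection can lengthen the median compared with letting the clock run.

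**Conclusion.** The point holds in a limited form. Death is not a DOR event under either set of criteria. Under irRC, a progression not re-assessed before a switch of therapy, withdrawal or death does not meet the written definition, and the relaxed analysis in SAP 1.9.3 does not cover it. Where such cases occur, DOR can be overstated: by half (6 to 9 months) in the assumed four-responder set, and not at all if the lost event is late.

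It would go too far to say that durability is overstated in this trial. No document reports a death or an unconfirmed irPD among responders, and with none there is no effect. The size rests on assumed durations and an assumed count of about four responders. The absence of a rule for later therapy or resection is a real omission, but not an upward bias. This is a worthwhile correction to an exploratory endpoint, not a threat to the trial's main conclusion.

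**What to change.** - **SAP 1.4.2:** define DOR, for both irRC and RECIST 1.1, as the time from first response to the earlier of progression or death from any cause. Correct the abbreviation in 1.6.2.
- **irRC only:** count an unconfirmed irPD as an event, dated at first detection, when new anticancer therapy, withdrawal or death precedes a repeat assessment. At the least, run this as a sensitivity analysis beside 1.9.3.
- **Later therapy, resection and loss to follow-up:** state which rule applies. Do not present censoring at new therapy as removing an upward bias; it is a trade-off, and such censoring may itself be informative.
- **Listing:** show each responder's DOR with the reason it ended or was censored. With so few responders this is more informative than a median.

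Cost: wording and one listing. Protocol 11.3 already provides for following survival, progression and subsequent treatment. Reported DOR may shorten. The change should be documented in the supplemental SAP that SAP 1.0 provides for, before final database lock. Because the study is open-label and the SAP describes enrolment and dosing in the past tense, the record should say that the rule was set after treatment.

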1.5 ANALYSIS POPULATIONS

1.5.1 SAFETY ANALYSIS POPULATIONS

The ASaT population will include all patients who received at least one dose of PVSRIPO and will be used for the analysis of safety data. At least 1 laboratory or vital sign measurement obtained

after at least 1 dose of study treatment is required for inclusion in the analysis of each specific parameter in the ASaT population. To assess change from baseline, a baseline measurement is also required.

1.5.2 EFFICACY ANALYSIS POPULATIONS

The FAS population, which consists of subjects who receive at least 1 dose of PVSRIPO and with measurable disease at baseline, will serve as the primary population for the analyses of efficacy data.

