## **8.9 DEFINITION OF EVALUABLE SUBJECTS, ON STUDY, AND END OF STUDY**

Any patient that receives at least one PVSRIPO injection will be evaluable for toxicity and efficacy analyses. Any patient that does not receive PVSRIPO injection will be withdrawn from the study and replaced.

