### 10.1 INCLUSION CRITERIA

1. Undergone prior vaccination against PV and received a boost immunization with trivalent IPOL® (Sanofi-Pasteur SA) at least 1 week, but less than 6 weeks, prior to administration of PVSRIPO (within 6 months of PVSRIPO retreatment).
  - a. Note: Patients who are unsure of their prior vaccination status/who have not been vaccinated must provide proof of vaccination and/or evidence of anti-PV immunity prior to enrollment, as applicable.
2. The patient must have received a boost immunization with trivalent inactivated IPOL™ (Sanofi-Pasteur) at least 1 week prior to administration of the study agent.
3. Patient must have histologically proven unresectable, recurrent, melanoma, stage IIIB, IIIC, or stage IV (AJCC staging must be documented in patient's medical record, as determined by CT of the chest, abdomen and pelvis, and/or whole body PET scan, and MRI of the brain within 4 weeks prior to administration of study drug)
4. Patients with BRAF mutations, must have failed at least 2 lines of therapy, specifically one BRAF targeted therapy and at least one anti-PD-1 based therapy. For BRAF wild type, patients must have failed at least one anti-PD-1 based therapy.
5. Patient must be  $\geq 18$  years of age.
6. Patient must have an ECOG/Zubrod status of 0-1.
7. Patient's disease must be bi-dimensionally measurable by caliper or radiological method as defined in the irRC criteria.
8. At least 1 injectable cutaneous, subcutaneous or nodal melanoma lesion  $\geq 10$  mm in longest diameter, or multiple injectable melanoma lesions which in aggregate have a longest diameter of  $\geq 10$  mm (Cohorts 0, 3 and possibly 1). For cohorts where 2 or 3 injections are planned (Cohorts 1 and 2), the patient must have at least 2 injectable melanoma lesions (when 2 doses are planned) or  $\geq 3$  injectable melanoma lesions when at least 3 doses are planned in different lesions (Cohorts 2 through 4).
  - a. NOTE: PVSRIPO retreatment requires  $\geq 1$  lesions amenable to injection
9. At least one measurable lesion that will not be injected.
10. Serum lactate dehydrogenase (LDH) levels less than  $1.5 \times$  upper limit of normal (ULN)
11. Patient must have adequate bone marrow, liver and renal function as assessed by the following:
  - b. Hemoglobin  $> 9.0$  g/dl
  - c. White blood count (WBC) of  $> 2000$  m3
  - d. Absolute neutrophil count (ANC)  $> 1,000/\text{mm}^3$
  - e. Platelet count  $> 75,000/\text{mm}^3$

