#### Definitions:

**Index lesions:** Up to 6 cutaneous lesions and up to 5 metastases (no more than 2 visceral organs) can be chosen. The distribution of these index lesions should be representative of the subject’s overall disease status. Index lesions should be selected on the basis of their size (lesions with longest bi-dimensionally perpendicular diameters) and suitability for accurate repeated measurements by imaging techniques (CT, MRI or ultrasound) and/or other method such as clinical exam. The sum of the products of the two largest of perpendicular diameters (SPD) of all index lesions will be calculated and reported.

**Measurable Disease:** Measurability is defined by the ability to measure a lesion bi- dimensionally with surface area determined by multiplying the longest diameter by the diameter perpendicular to the longest diameter as defined below. An individual lesion measure is therefore provided by the product of a tumor’s longest diameter and the diameter perpendicular to that. All measurements will be determined using a ruler or calipers and reported in metric notation (mm) and will be recorded bi-dimensionally.

**Measurable Lesions:** Measurable lesions are defined at baseline as lesions that can be accurately and serially measured in at least 2 dimensions and for which the longest diameter is:

- $\geq 10$  mm as measured by CT scan, MRI, or ultrasound for nodal/soft tissue disease (including lymph nodes)
- $\geq 10$  mm caliper measurement by clinical exam for superficial cutaneous or subcutaneous melanoma lesion as measured by caliper

- multiple superficial melanoma lesions which in aggregate have a total diameter of  $\geq 10$  mm

**Non-measurable Lesions:** All other lesions, including small lesions (longest diameter  $< 10$  mm by CT/MRI/ultrasound for nodal/soft tissue disease [including lymph nodes] or  $< 10$  mm caliper measurement by clinical exam for superficial cutaneous melanoma lesion) and other truly non-measurable lesions are considered non-measurable and characterized as non-index lesions. This will include any measurable lesions beyond the maximum number of 5 lesions that were not chosen as index lesions.

**Follow-up “Index Lesions”:** At each subsequent tumor assessment, the SPD of the index lesions are added together to provide the total tumor burden.

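### The SAP's efficacy population adds a measurable-disease condition, under a stricter definition than the one used at enrolment, so an eligible treated patient could fall out of the ORR denominator

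*SAP*

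**What the plan says.** **Who counts for efficacy.** Protocol 8.9 states: "Any patient that receives at least one PVSRIPO injection will be evaluable for toxicity and efficacy analyses". It sets no condition on measurability. SAP 1.5.2 defines the Full Analysis Set (FAS) as "subjects who receive at least 1 dose of PVSRIPO and with measurable disease at baseline", and SAP 1.6.2 uses the FAS for the overall response rate (ORR). Protocol section 14 gives the SAP precedence where the two differ, so the narrower set governs.

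**What measurable means at enrolment.** Protocol 11.7.1 (Definitions) asks for lesions that can be "measured in at least 2 dimensions and for which the longest diameter is" at least 10 mm, lymph nodes included. It also accepts "multiple superficial melanoma lesions which in aggregate have a total diameter of" at least 10 mm. Inclusion criterion 8 (Protocol 10.1) admits patients on one lesion of that size, "or multiple injectable melanoma lesions which in aggregate have a longest diameter of" at least 10 mm, and names Cohorts 0 and 3, and possibly 1, for that criterion.

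**What measurable means in the SAP.** SAP 1.9.1 says: "Both the longest diameter and the longest perpendicular must be greater than or equal to 10 mm or 2 times the axial slice thickness", taking the greater of the two. For nodes it says: "Lymph nodes must have a short-axis line-length of" at least 15 mm. It gives no route for clusters. Its list of non-measurable disease includes masses whose longest uninterrupted diameter or perpendicular falls below the threshold.

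**When the rule was written.** The SAP is undated but describes enrolment in the past tense, and section 1.5.3 reports that nobody entered Cohort 4 or was retreated. SAP 1.2 says that sponsor personnel knew treatment assignments. Protocol 6.2.4 had already reported an objective response in injected lesions in 4 of 12 patients.

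**The concern.** The two documents give different denominators for the main efficacy estimate, and the one that takes precedence rests on a tighter definition than the one patients were enrolled under. A patient can be eligible, injected and efficacy-evaluable under the protocol, yet not belong to the FAS. SAP 1.6.2 counts patients without response data as non-responders, but that rule works inside the FAS and cannot bring back someone who never entered it.

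With 12 treated patients, each one carries about 8 percentage points of the denominator (1/12 = 8.3%). The rule also appears in a document written once some results were visible in an open-label trial. Even if it was chosen for good reasons, a reader cannot rule out that the results influenced it. An all-treated denominator leaves no such doubt.

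**Working it through.** **Step 1. Reproduce the treated number.** SAP 1.1 gives 4 cohorts of 3 subjects: 4 × 3 = 12. This matches the total stated there and is the largest possible ORR denominator.

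**Step 2. Compare the definitions.**

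| Baseline lesion | Protocol 11.7.1 / criterion 8 | SAP 1.9.1 |
|---|---|---|
| Nodule 12 × 7 mm | Measurable (12 ≥ 10) | Not measurable (7 < 10) |
| Lymph node, longest diameter 12 mm | Measurable (12 ≥ 10) | Not measurable (short axis at most 12, below 15) |
| Superficial cluster, each lesion under 10 mm, total at least 10 mm | Measurable as an aggregate | Not measurable (each lesion under 10 mm, no aggregate route) |

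The lesion sizes are hypothetical. The SAP is stricter on the perpendicular diameter, the nodal short axis and clusters. The slice-thickness clause can raise the threshold further for imaged lesions.

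**Step 3. Ask when a patient, and not just a lesion, is lost.** FAS entry needs measurable disease somewhere, so one qualifying lesion is enough. A patient is excluded only if every baseline lesion fails SAP 1.9.1. Inclusion criterion 7 (bi-dimensionally measurable disease) and criterion 9 (a measurable lesion that will not be injected) make this less likely. Neither prevents it, because neither requires both diameters to reach 10 mm or a node to reach 15 mm in short axis.

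**Step 4. Size, for illustration only.** The inputs are 12 treated patients (SAP 1.1), 4 with a response in injected lesions (Protocol 6.2.4), and the exact binomial 95% interval (SAP 1.6.2). The number excluded is not in the documents; 0 to 3 is an assumption. For x responders in n, the exact limits are:

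- lower = 2.5% quantile of Beta(x, n − x + 1)
- upper = 97.5% quantile of Beta(x + 1, n − x)

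For 4/12 these are Beta(4, 9) and Beta(5, 8), giving 9.9% and 65.1%. The binomial tail probability at each limit is 0.025, as it should be.

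| Assumed exclusions | ORR | Exact 95% CI |
|---|---|---|
| None | 4/12 = 33.3% | 9.9-65.1 |
| 1 non-responder | 4/11 = 36.4% | 10.9-69.2 |
| 2 non-responders | 4/10 = 40.0% | 12.2-73.8 |
| 3 non-responders | 4/9 = 44.4% | 13.7-78.8 |
| 1 responder | 3/11 = 27.3% | 6.0-61.0 |

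Across these cases each excluded non-responder adds about 3 to 4 points, and one excluded responder removes about 6.

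**The case against.** The strongest reply is that nothing shows a patient was lost. Neither document gives the FAS size or any baseline lesion dimensions. Criteria 7 and 9 required measurable disease, including a lesion left uninjected, so all 12 may meet the SAP definition. This stands: the exclusion is possible but not documented.

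Second, requiring measurable disease for a response rate is common practice, and SAP 1.5.2 does not say which definition it means. The slice-thickness wording in 1.9.1 suits imaging, while the same section provides for cutaneous index lesions. This stands in part. The link between the two sections is an inference, but 1.9.1 holds the only definition the SAP writes out, and a programmer building the FAS would have to use it.

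Third, efficacy is exploratory (SAP 1.4.2), no inference is to be drawn (SAP 1.1 and 1.8), and the shifts above are small against an interval about 55 points wide (65.1 − 9.9 = 55.2). This stands and lowers the severity. It does not remove the conflict.

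Three stronger readings are tempting, and the documents do not support them:

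- **That exclusions depend on outcome.** Measurability is a baseline attribute. What can be said is that the rule was written when some results were visible.
- **That the rule inflates the ORR.** The illustration moves both ways. Its numerator is response in injected lesions, not overall response by the immune-related criteria (irRC).
- **That the stricter definition removes lesions from the tumour sum of patients who stay in.** SAP 1.9.1 works from target lesions selected at baseline and does not say that they are to be re-selected.

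**Conclusion.** The conflict is real and lies in the written rules. SAP 1.5.2 narrows the efficacy population set by Protocol 8.9, and SAP 1.9.1 defines measurable disease more strictly than Protocol 11.7.1 and inclusion criterion 8. An eligible, treated patient could therefore leave the ORR denominator if none of their baseline lesions meets the SAP definition. The number affected may be zero, and the direction of any effect is unknown.

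Under an assumed 0 to 3 exclusions, and with the injected-lesion count standing in for the irRC numerator, the ORR would lie between 27.3% and 44.4%, against 33.3% for all treated. The conclusion assumes that 1.5.2 uses the definition in 1.9.1. If it does not, the difference from Protocol 8.9 remains and the governing definition is unstated.

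Severity is moderate: efficacy is exploratory, and the primary DLT endpoint uses all treated subjects (SAP 1.5.1) and is unaffected.

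**What to change.** - **SAP 1.5.2:** define the primary ORR population as all subjects who received at least one injection (n = 12, as in Protocol 8.9), with subjects who lack an evaluable response counted as non-responders.
- **SAP 1.9.1:** align the baseline measurable-disease definition with the measurable-lesion definition in Protocol 11.7.1: longest diameter at least 10 mm by caliper or imaging, nodes included, clusters allowed. Take over that definition only. The limits on the number of index lesions differ within Protocol 11.7.1 itself (up to 6 cutaneous plus up to 5 metastases in one place, a maximum of 5 in another) and should be reconciled separately.
- **If the stricter definition is kept:** report it only as a sensitivity analysis, with the number of patients excluded and the reason for each, beside the all-treated ORR.

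The cost is two SAP paragraphs and no new data. If nobody fails the stricter definition, the denominator is unchanged. If non-responders would have been excluded, the ORR will be slightly less favourable than the FAS figure.
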